During a review of diagnoses at the neurology clinic at Norrland University Hospital (NUS) between 01/01/2006 and 30 June 2012, we found on average 7.8 cases of PLPH (G97.0 - leakage of spinal fluid after LP) per year, and about 6 care days per year. An inpatient day costs SEK 7713, which means a total cost for care days of approximately SEK 50,000. This only includes the worst cases PLPH. Many more episodes of PLPH are likely to occur without being noted by the health care, and we don't know how many sick leave days/year occur due to PLPH.

It is possible to reduce the risk of PLPH. The American Academy of Neurology (AAN) notes that there is strong scientific support (class 1 evidence) that:

1. Needle size is important. The smaller the needle, the less PLPH.

2. A cutting needle should be inserted with the cutting edge parallel to the dural fibers to reduce the incidence of PLPH.
3. Non-cutting needles (atraumatic) reduce the risk of PLPH, as compared to cutting needles of the same size.
4. Re-insertion of the stylet into an atraumatic needle before needle withdrawal reduces the risk of PLPH. However, this has only been shown in one study. It has not been studied if PLPH can be prevented by reinserting the stylet in cutting needles.

In recommendations published in Läkartidningen (LT) 2008, it appears that a thin non-cutting needle (0.4 mm / 27G) works well in a neurologist clinic in Stockholm. Despite this, and despite the strong recommendations issued by AAN as stated above, it is still common that large (0.9 mm/20G), cutting needles are used at our clinic (personal communication, LP assistants, 2013). One factor that can affect the propensity to use atraumatic needle is the price: one needle costs about 50 SEK compared to a cutting needle that costs about SEK 10. Interestingly enough, the recommendation to reinsert the stylet into non-cutting needle is not included in the article in the LT, even though the AAN recommendations are very clear on this matter. This suggests that one single study is not accepted as evidence enough to change practice, and justifies that we study this in our study.

Other factors that may affect the risk of PLPH are the patient's age, BMI, sex, LP position (sitting/lying down), CSF volume drawn and if the LP is "traumatic" (i.e., associated with blood-mixed CSF).

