### **Purpose and method**

The purpose of this study is to investigate how three different needles work with regard to usability, time efficiency and PLPH incidence in the clinic. The needles included are:

1. Sprotte 25G (0.5 mm) atraumatic with introducer
2. Sprotte 22G (0.7 mm) atraumatic with introducer
3. Spinocan 25G (0.5 mm) cutting

Rationale for the choices of needles: If the PLPH incidence is already low when using cutting 25G needle, and does not significantly decrease when using the same size atraumatic needle, it may be health economically reasonable to choose the former because of lower price and no need to anesthetize before insertion (the needle is not thicker than the anesthetic needle, and it is mainly penetration of the skin that feels uncomfortable). The larger (22G) atraumatic needle is included to examine the time saved (higher flow rate) when using it, and how much the PLPH incidence differs between it and the smaller one. If the PLPH incidence is very low already when using this larger needle, it can be argued not to go down further in size, as long as the time saving is large.

We also investigate whether reinserting the stylet before needle withdrawal reduces the frequency of PLPH by randomizing between reinserting it, or not, in all needle categories. Thus, there will be 6 different categories (3 needles x 2 stylet options). The patients will be randomized to either option using a computer program that block-randomizes (12 subjects/block, 2 of each needle/stylet category in each block). Randomization will occur stratified by gender, BMI above or below 25 and age over and below 50 years. This is to

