#### Power

Since the project's results can have immediate effects on how LP is performed both nationally and internationally, we have chosen to perform an interim analysis after 2 years of study duration (1/1 2016). If clear results appear already then, the project will be interrupted. If the study runs for the full 3 years, it is estimated to include approximately n = 900 patients. These will be randomized so that approximately n = 150 ends up within each needle / stylet category (n = 300 / needle). In power calculations we assume an alpha = 0.05, power = 80%, a chi-2 test to show differences between the groups, and 900 participants. With regards to the difference between needles, it has previously been shown that LP with a non-cutting needle (22G) gave a PLPH incidence of 12.2%, compared to cutting (22G) 24.4%. To detect this difference, power calculations suggest n = 157 individuals in each group (we will have n = 300 after 3 years, n = 200 after 2 years). The difference in PLPH frequency between reinserting the stylet or not was 5% vs. 16% with a non-cutting 21G needle. Such a difference would require n = 121 patients in each group (we will have n = 450 after 3 years, n = 300 after 2 years). Size: The frequency PLPH with 24–27G needle is 5–12%, and for needles in sizes 20–22G 20–40%. To detect the smallest possible difference (20% vs. 12%) we would need n = 329 patients (we will have n = 300 after 3 years, n = 200 after 2 years).

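### Randomisation uses sex, BMI, age and a needle-by-stylet crossing, but no PLPH analysis is named that uses them; the chi-2 assumed for power is valid but mildly conservative

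*Combined protocol and SAP*

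**What the plan says.** Under Purpose and method, the combined protocol and SAP says "Randomization will occur stratified by gender, BMI above or below 25 and age over and below 50 years", in blocks of 12 with two patients per needle/stylet category. The stated reason is balance across categories. The Background lists "age, BMI, sex, LP position (sitting/lying down), CSF volume drawn" among factors that may affect PLPH risk. It also says of stylet reinsertion: "It has not been studied if PLPH can be prevented by reinserting the stylet in cutting needles".

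The only test named is in the Power section: "In power calculations we assume an alpha = 0.05, power = 80%, a chi-2 test to show differences between the groups". There the comparisons are treated one at a time, with about 300 patients per needle and 450 per stylet option. The same section says "we have chosen to perform an interim analysis after 2 years of study duration", with the project to stop if results are clear. From Background to Report there is no stratified or regression analysis of PLPH, no analysis that contains both randomised factors, and no needle-by-stylet check.

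**The concern.** Stratified blocks remove some chance variation between the arms. An unadjusted chi-2 still counts that variation in its standard error. If the stratifying factors or the stylet affect PLPH, the test then rejects less often than its nominal 5%, loses a little power, and has intervals that are slightly too wide.

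The direction is not neutral. Purpose and method reasons that, if PLPH is already low with the cutting 25G needle and "does not significantly decrease when using the same size atraumatic needle, it may be health economically reasonable to choose the former". A conservative test makes that non-significant outcome slightly more likely. Separately, a stylet comparison pooled over needles averages over any difference between cutting and atraumatic needles, although the Background itself notes that reinsertion is unstudied in cutting needles.

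**Working it through.** **1. The plan's own figures.** With n = [1.96·√(2p̄(1−p̄)) + 0.842·√(p₁(1−p₁)+p₂(1−p₂))]² / (p₁−p₂)²:
- 24.4% vs 12.2%: (1.0718 + 0.4545)²/0.122² = 156.5, so 157.
- 16% vs 5%: (0.8497 + 0.3589)²/0.11² = 120.7, so 121.
- 20% vs 12%: (1.0162 + 0.4337)²/0.08² = 328.5, so 329.

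All three match the Power section. The calculation is therefore a plain two-sided, two-group chi-2 with no term for strata or for the other factor. At the planned sizes its power is 97.3%, 99.97% and 76.3%.

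**2. Why chi-2 is conservative.** Take a common rate of 16%, the mean of 20% and 12%. The chi-2 variance per patient is 0.16 × 0.84 = 0.1344. With needles balanced within the 16 cells (8 strata × 2 stylet options), the true variance is 0.1344 minus the variance of the cell risks.
- *Stylet only.* The stylet odds ratio is (0.16/0.84)/(0.05/0.95) = 3.62, from "5% vs. 16% with a non-cutting 21G needle". The cell risks are 8.02% and 23.98%, with variance 0.0064. The SE ratio is √(0.1280/0.1344) = 0.976, the effective critical value is 1.96/0.976 = 2.008, and type I error is 4.5%.
- *Stylet plus assumed sex/BMI/age odds ratios of 3/1.5/3.* The variance of the cell risks is 0.0164. The SE ratio is √(0.1180/0.1344) = 0.937, the critical value is 2.092, and type I error is 3.6%.

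Simulation with the plan's blocks, including incomplete last blocks (100,000 trials per scenario), gives 4.54% and 3.61%. CMH gives 5.07% and 4.90%.

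**3. Power (same simulation; Monte Carlo SE about 0.13 points).** CMH is stratified by sex, BMI group, age group and stylet.

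| Comparison | Prognostic assumption | Chi-2 % | CMH % | Gain, points |
|---|---|---|---|---|
| 20 vs 12%, 300 per needle | none | 76.72 | 76.66 | −0.06 |
| | stylet OR 1.5 | 76.81 | 76.88 | +0.07 |
| | stylet OR 2 | 77.15 | 77.53 | +0.38 |
| | stylet OR 3.62 | 77.20 | 78.56 | +1.36 |
| | strata 3/1.5/3 | 77.45 | 79.73 | +2.28 |
| | both | 78.23 | 81.79 | +3.56 |
| 20 vs 12%, 200 per needle (interim) | none | 59.16 | 58.98 | −0.18 |
| | stylet OR 3.62 | 59.70 | 61.23 | +1.53 |
| 24.4 vs 12.2%, 300 per needle | stylet OR 3.62 | 97.80 | 98.06 | +0.26 |
| 12 vs 6% (assumed), 300 per needle | stylet OR 3.62 | 74.29 | 75.10 | +0.81 |
| | both | 74.71 | 77.16 | +2.45 |

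In the last two rows, non-significance falls from 25.7% to 24.9% and from 25.3% to 22.8%.

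**4. Intervals (20% vs 12%, stylet OR 3.62).** The unadjusted and standardised risk differences have the same true SD, 2.90 points. The unadjusted SE averages 2.97 and the standardised SE 2.89 (2.97/2.89 = 1.03). Nominal 95% intervals cover 95.5% and 94.9%. With the strata effects added, the unadjusted interval covers 96.3%.

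**5. Why name one analysis in advance.** Chi-2 and a logistic likelihood-ratio test disagree on significance at 20% vs 12% in 0.4% of trials if nothing is prognostic, 1.8% with the stylet effect and 4.0% with both.

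**6. Interaction (60,000 trials; atraumatic 25G at 12%, 22G at 20%, cutting 25G at 12% or 20%).** If the stylet odds ratio is 3.62 in atraumatic needles and 1 in the cutting needle, the pooled odds ratio is 2.45 or 2.16, and the interaction test has 84% or 92% power. With odds ratios of 2 and 1, its power is 38% or 47%.

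**The case against.** The strongest reply is that nothing is broken. Balance was the stated purpose of the strata, stratified blocks deliver it, and a valid unadjusted test is a legitimate choice. The gain also rests on assumptions: one result with a non-cutting 21G needle is carried over to all needles, and the sex, BMI and age odds ratios have no source in the documents. With stylet odds ratios of 1 to 2 and no stratum effects, the gain is −0.1 to 0.4 points. The comparisons at 24.4% vs 12.2% and 5% vs 16% have almost nothing to gain. All of this stands, and it limits the point to a cheap improvement.

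It does not remove the point. The plan treats age, BMI and sex as possible risk factors and uses them to randomise, yet does not say whether the analysis uses them, and results may stop the study at two years.

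A reader might infer that the chi-2 is an error or that leaving the choice open seriously inflates false positives. Neither follows. The chi-2 errs on the conservative side, and taking the smaller of the chi-2 and logistic p-values gives a type I error of only 5.0–5.2% at a 16% rate.

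**Conclusion.** The point holds as an improvement. The randomisation factors have no stated role in the PLPH analysis, and the one test named is valid but mildly conservative if they matter. For 20% vs 12%, its type I error is about 4.5% under the stylet assumption and 3.6% with 3/1.5/3 added. Stratifying gains about 0, 1.4 or 3.6 points, depending on what is prognostic. These are ranges, not estimates.

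Two further inferences are not supported. Adjustment does not reliably close the gap between 300 and 329 per group: power passes 80% only in the most favourable row of the table. Nor does it turn a non-significant cutting-versus-atraumatic result into evidence of equivalence. It makes that outcome only 0.8 to 2.5 points less likely at the assumed 12% vs 6%.

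**What to change.** Before the 2-year interim analysis, name one primary PLPH analysis for both looks:
- Test each needle comparison by CMH stratified by sex, BMI group, age group and stylet. Test the stylet comparison by CMH stratified by sex, BMI group, age group and needle.
- Report risk differences with 95% CIs standardised from a logistic model with needle, stylet, sex, BMI group and age group. Average the predicted risks over all patients under each option.
- Keep the unadjusted chi-2 as supporting.
- Report the needle-by-stylet interaction as exploratory, with the stylet effect shown separately for cutting and atraumatic needles. Its power for moderate differences is too low for a confirmatory role.

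The cost is one analysis paragraph, with no new data or patients, and at most about 0.2 points of power if nothing is prognostic. CMH is preferable to a logistic likelihood-ratio test for the p-value. At a 5% rate with 200 per needle, the likelihood-ratio test has a type I error of about 5.5%, against about 5.0–5.1% for CMH. Its extra 0.06 to 0.8 points of power over CMH is not a gain from adjustment.

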## **Background**

Lumbar puncture (LP) with spinal fluid analysis (CSF analysis) is a common procedure at neurological clinics. At the neurology clinic in Umeå, about 250-300 LP is carried out every year at a specialized LP lab, and an additional 50 LP at the ward (usually on on-call time when the LP-lab is closed). Common indications include suspected bleeding, infection, inflammation, neurodegenerative processes and CSF pressure measurement.

A relatively common complication after LP is post-LP headache (PLPH). This complication occurs in between 20 and 30% of all who have undergone an LP. It is characterized by being positional, i.e. worsens in standing (within 15 minutes after standing up) and improves/completely resolves upon lying down (within 15 minutes after lying down). PLPH occurs within 5 days of LP, and disappears within 1 week of occurrence. The headache is often associated with one of the following: neck stiffness, tinnitus, mildly impaired hearing, photosensitivity, nausea. (See International Headache Society's definition: <http://ihs-headache.org>). It is not known today why PLPH occurs, but a commonly adopted theory is that there is a leakage of CSF through the hole that has been made, which thus causes low hydrostatic pressure in the central nervous system (CNS). This either causes a painful vasodilation of veins within the CNS or traction of the pain-sensitive meninges, or both. Recommendations for relieving PLPH usually include bed rest (when PLPH has occurred - there is no evidence that bed rest prevents the occurrence of PLPH), fluid intake, caffeine intake and common analgesics. As a curative treatment in difficult-to-treat cases, one may administer a bloodpatch, which means that 15-20 ml of autologous blood is injected into the epidural space, preferably at the same level as the original LP. This is believed to have the effect of both clogging the leaking hole (platelet plug), and exerting a pressure on the spinal cavity, which increases the pressure in the CNS and thus reduces the effect of the lost amount of CSF.

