ensure an even distribution of these baseline characteristics across each needle/stylet category. People who undergo LP at the neurological clinic, NUS during a 3-year period (from January 1, 2014 - December 31, 2016), and who are judged to be able to answer the follow-up questions, will be asked about participation. Data is collected during the LP itself, and at a follow-up telephone call by a blinded nurse at the neurology outpatient clinic 5 days after LP, repeated after 5 days if still having PLPH. The more exploratory parameters that are investigated are whether the opening CSF pressure is important for the risk of PLPH, and whether the volume of CSF drawn is of importance for the risk of PLPH. In addition to this, data on the intensity of the headache as well as possible sick leave are registered. As a welcome side effect of the study, we also hope that the use of small non-cutting needles increases in the clinic with reduced occurrence of PLPH as a result. A challenge lies in instructing medical student who perform many of our LPs in the use of these needles, and this parameter is also interesting to study. One of the strengths of the study is that the setting is "real life" with several different operators, supervision of medical students and an unselected patient material. We believe this may increase the external validity of the study results.

In parallel with the study, an anonymous, web-based questionnaire will be distributed via e-mail to the members of the Swedish Neurologist Association. In this questionnaire, the respondent's current approach to routine lumbar puncture (needle type, size, stylet reinsertion or not, and knowledge of AAN's guidelines) is requested. These data, together with the study results, will form the basis for health-economic calculations on various lumbar puncture strategies in Sweden, and will be used primarily in connection with the study results being reported in the form of a debate entry in e.g. Läkartidningen.

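### The only routine follow-up call falls on the last day of the plan's 5-day onset window, so PLPH starting after the call is not recorded; the loss is probably small and is avoided by calling after the window closes

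*Combined protocol and SAP*

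**What the plan says.** The Background describes the endpoint: "PLPH occurs within 5 days of LP, and disappears within 1 week of occurrence". Purpose and method names two points at which data are gathered: "Data is collected during the LP itself, and at a follow-up telephone call". That call is made by "a blinded nurse at the neurology outpatient clinic 5 days after LP, repeated after 5 days if still having PLPH".

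The repeat call therefore depends on headache being present at the first one. The combined protocol and SAP describes no diary, no instruction to phone in about a later headache, and no second contact for a patient who is well on day 5. It does not give the hour of the call or an allowed range of days, and it does not say whether day 5 counts in full.

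The sample size reasoning is under Power: "we assume an alpha = 0.05, power = 80%, a chi-2 test to show differences between the groups, and 900 participants". It works from incidence alone.

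**The concern.** The call coincides with the end of the period in which the endpoint can occur. If the window includes all of day 5, a patient called that morning who develops a positional headache that evening meets the plan's description but is counted as having had no event. If calls are sometimes made early, more of the window goes unobserved.

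Two things are at stake. First, lower recorded rates in every arm shrink the absolute differences and cost some power. Second, absolute incidence matters here in its own right: the needle rationale turns on whether incidence is already low with a given needle, and the results are to feed health-economic calculations. Under-counting lowers those figures even when it is equal across arms.

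A separate, smaller point concerns duration. An episode starting on day 5 can run to day 12 under the plan's description, but the repeat call comes at about day 10.

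**Working it through.** **Step 1: timing, from the plan's own statements.**

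- Onset window: LP to day 5 (Background).
- Routine call: day 5 (Purpose and method).
- Part of the window not covered: from the call to the end of day 5, under 1 day of 5. If the window means exactly 120 hours and the call comes at or after that hour, the gap is zero.
- Headaches that began and resolved before the call can still be reported, so they are not lost.
- Latest end of an episode: 5 + 7 = day 12. Repeat call: 5 + 5 = day 10.

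**Step 2: reproduce the plan's sample sizes.**

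Inputs from Power: 24.4% vs 12.2% (needle type), 16% vs 5% (stylet), 20% vs 12% (needle size), alpha 0.05, power 80%, chi-square test. Sidedness is not stated; two-sided reproduces the plan's figures and one-sided (124, 95, 259) does not. With p̄ the mean of the two rates,

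n per group = [1.960·√(2p̄(1−p̄)) + 0.842·√(p1(1−p1) + p2(1−p2))]² / (p1−p2)²

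For 20% vs 12%, p̄ = 0.16, so n = (1.0162 + 0.4337)² / 0.08² = 328.5, rounded up to 329. The other two comparisons give 156.5, so 157 (the plan: "power calculations suggest n = 157 individuals in each group"), and 120.7, so 121 (the plan: "Such a difference would require n = 121 patients in each group"). All three match, with 329 read as per group.

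**Step 3: effect of missed cases.**

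Let f be the share of PLPH cases that start after the call. The documents give no onset distribution, so f is an assumption, taken as equal in both groups. Each rate is multiplied by (1−f). As a guide to scale, f = 10% corresponds to onset spread evenly over 5 days with the call half a day before the window closes (0.5/5). Onset concentrated in the first days would give a smaller f.

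Power = Φ{[(p1−p2)√N − 1.960·√(2p̄(1−p̄))] / √(p1(1−p1) + p2(1−p2))}, with N the 3-year number per group (300 per needle, 450 per stylet group).

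Example, needle size with f = 5%: rates 0.190 and 0.114, p̄ = 0.152.

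- n = (0.9951 + 0.4249)² / 0.076² = 349.1, rounded up to 350.
- Power at N = 300 = Φ[(1.3164 − 0.9951) / 0.5049] = 73.8%.

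| Comparison (N per group) | | f = 0 | 2% | 5% | 10% |
|---|---|---|---|---|---|
| Needle size, 20% vs 12% (300) | n needed | 329 | 337 | 350 | 373 |
| | power | 76.3% | 75.3% | 73.8% | 71.0% |
| Needle type, 24.4% vs 12.2% (300) | n needed | 157 | 161 | 167 | 178 |
| | power | 97.3% | 97.0% | 96.5% | 95.4% |
| Stylet, 16% vs 5% (450) | n needed | 121 | 124 | 128 | 136 |
| | power | >99.9% | >99.9% | >99.9% | >99.9% |

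**Step 4: effect on incidence.**

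Under equal f the ratio of the two rates is unchanged and each absolute rate falls by the factor (1−f). A true 12% is recorded as 11.8%, 11.4% or 10.8% at f = 2%, 5% or 10%.

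**The case against.** A reader might infer that late-onset PLPH as a class is missed. The documents do not support that. By the plan's own description, almost the whole window has passed at the call, and headache starting after day 5 is not PLPH under that description, so it is not a lost endpoint. Only the remainder of day 5 is exposed.

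A reader might also infer bias between needles or stylet arms. The caller is blinded and the schedule is the same in every arm, so any loss should be largely non-differential. It would differ only if onset timing differed by arm, and the documents give no data on that.

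The size of the loss is assumed throughout. The power effect is visible mainly in the needle-size comparison, which is already short on the plan's own figures (329 needed, 300 available). The other two comparisons have ample margin.

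Weekends are a third temptation. After a Monday or Tuesday LP, day 5 is a Saturday or Sunday. If the nurse works weekdays only and calls on the Friday before, 1-2 days of the window go unobserved. Both conditions are assumptions: nothing says calls are weekday-only or brought forward, and a move to Monday would cover the full window. What stands is that the plan sets no earliest call time, so it does not rule out early calls.

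Finally, the day-10 repeat call bears on duration only. It does not affect the incidence comparison on which the power calculations rest.

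These objections limit the size of the point. They do not remove the gap: a patient who is well at the call has no later contact, and part of day 5 may lie after it.

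**Conclusion.** The point holds as a minor weakness in the follow-up schedule. The routine call is placed on the last day of the onset window with no later contact for patients who are well, so onset after the call is unrecorded. The loss is probably small and largely equal across arms.

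Under assumed losses of 2% to 10%, needle-size power falls by 1.0 to 5.3 percentage points (76.3% to 75.3%, and to 71.0%), while the needle-type and stylet comparisons remain well powered. The main consequence is a slightly understated absolute incidence. The plan's stated sample sizes are reproduced and are not in question. The conclusion on timing rests on the documents alone; every figure for its effect rests on the assumed f.

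**What to change.** Make the routine call after the window has closed, for example on day 7, and state that it is never made before 5 full days have passed. Ask specifically about headache onset on days 0-5, so that later headaches are not counted. Day 7 is the same weekday as the LP, which avoids the weekend question for weekday procedures. For an LP done at a weekend, allow the next working day, not an earlier one.

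If headache is still present, make the repeat call on or after day 12. Day 12 itself falls on the same weekday as day 5 and so brings the weekend problem back; day 14 is again the weekday of the LP. This lets a day-5 onset be assessed against the 1-week duration criterion.

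The number of calls is unchanged. The cost is about two more days of recall at the first call, for onset, positional character and intensity. If the day-5 call is kept, the minimum is a stated earliest call time of 5 full days after LP.
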